# Cancelled cycles and trial data

When cycles are cancelled it will be at the discretion and cost of the provider (treatment centre) as to whether a complimentary cycle is offered. Any replacement cycles will be recorded as non-trial treatments.

# 8. OUTCOME MEASURES

### 8.1. Internal pilot outcomes

The decision to continue to a full trial will be based on pre-defined stop-go criteria, and informed by the findings from the pilot qualitative process evaluation.

Related to the objectives in section 2.1, the outcomes for the pilot are the number of randomised participants and number of sites open at the end of the pilot phase. The aim of the pilot is to enrol at least 176 couples and open at least 12 centres, as set by the trial Funder (see Table 1).

The decision of whether to progress from the internal pilot to the full trial will largely be based on the recruitment outcome, as this is expected to be the most challenging aspect of the trial. If recruitment is ≥100% of expected (green in Table 1), UNITY will proceed to the main trial on discussion with the Funder. If recruitment is 67-99% of expected (amber), the trial team will explore and implement methods with the Trial Steering Committee (TSC) and the Funder to improve recruitment; if recruitment is <67% of expected (red), with no obvious remedial factors, there will be discussions with the TSC and the Funder around stopping the trial (see Table 1).

Any decision regarding the feasibility and acceptability of the RCT, and remedial measures, if necessary, will also be informed by the results from the embedded qualitative process evaluation.

Table 1: UNITY Internal Pilot Targets

	Red	Amber	Green
Trial recruitment n (%)	<118 (<67)	118-175 (67-99)	≥176 (100)
Recruitment rate/ site/ month	<1.6	1.6-2.3	2.4
Number of sites opened	<8	8-11	≥12

### 8.1.1. Qualitative

- A qualitative assessment of UNiTY's feasibility, acceptability and appropriateness for couples and HCPs.
- To dynamically inform decision making as to whether UNiTY should proceed to the next evaluative phase (e.g., continue to a full trial, refine the study design, or stop the trial).
- For further information please see Section 16.1.

#### 8.2. Main trial outcomes

#### 8.2.1. Primary outcome

The primary outcome is the live birth of a baby at ≥34 week's gestation, conceived within 270 days of randomisation (approximately 9 months). Date conceived is determined as date of egg collection for couples who have undergone fresh embryo IVF, date of embryo transfer minus the number of days of culture for couples who have undergone frozen embryo IVF, date of insemination for couples who have undergone IUI, and 14 days after the first day of the last period for couples who have conceived naturally.

In line with the evaluation of treatment policy, initial or subsequent pregnancies may be included within this timeframe. This outcome will be assessed at 19 months post-randomisation.

\_\_\_\_\_\_

### 8.2.2. Secondary outcomes

#### 8.2.2.1. Clinical

#### **Pregnancy outcomes**

The following outcomes will be assessed at two time points: 19 months post-randomisation to allow for pregnancy outcomes to be obtained and concern pregnancies conceived within 270 days (approximately 9 months) of randomisation; and 25 months post-randomisation to allow for pregnancy outcomes to be obtained and concern pregnancies conceived within 450 days (approximately 15 months) of randomisation. This will enable us to determine the medium-term effect of the initial treatment policy decision.

- Singleton live birth ≥37 weeks;
- TTP leading to a live birth defined as time from randomisation to pregnancy in days (censored at 270 days);
- Cycle cancellation and reason (failure to respond / over-response);
- Biochemical pregnancy;
- Clinical pregnancy;
- Ongoing pregnancy at 12 weeks (range 11 to 14 weeks);
- Multiple pregnancy;
- Ectopic pregnancy;
- Miscarriage (defined as delivery before 24 weeks of gestation);
- Stillbirth (defined as intrauterine death ≥24 weeks);
- Termination:
- Number of embryos remaining (IVF group).

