# 2.2. Main trial objectives

### 2.2.1. Clinical aims and objectives

The primary objective is to test the hypothesis that in couples with UEI, the policy of offering three cycles of IUI is not substantially worse than the policy of offering IVF by up to a 10% margin of non-inferiority in terms of live birth \ge 34 weeks [MRC/NIHR framework, core element 4: uncertainties].

The secondary clinical objectives for the trial are:

- 1. To evaluate the rates of pregnancy loss for IUI versus IVF for couples with UEI.
- 2. To compare the health of babies born as a result of IUI versus IVF to couples with UEI.
- 3. To compare the complication rates of the two treatment arms.
- 4. To evaluate the TTP leading to a live birth for IUI versus IVF for couples with UEI.
- 5. To explore patient satisfaction in the two treatment arms.
- 6. To compare outcomes of couples over a longer period of 25 months post-randomisation when further interventions may have been provided.
- 7. To explore the different clinical features of IUI and IVF cycles.
- 8. To explore the reasons patients may not complete the full course of treatment or wish for different treatment options.

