### 14.2.2. Secondary outcomes

The secondary outcomes that are binary (i.e., yes/no) will be analysed using the same methods as described for the primary outcome (see Section 14.2.1), with corresponding 95% confidence intervals (this includes the longer-term assessment at 25 months). For those secondary outcomes that are continuous (e.g. Gestational age at delivery, Birthweight, CSQ-8 score), mixed effects linear regression methods will be utilised to calculate an adjusted mean difference and 95% confidence interval. Time-to-event outcomes (e.g. TTP leading to a live birth) will be analysed using a mixed effects ('frailty') Cox Proportional Hazard model, allowing the same minimisation variables as fixed effects and randomising centre as a random effect. The treatment effect will be expressed as adjusted hazard ratio with 95% confidence interval. Regarding safety, the total number of participants experiencing SAEs will be given by allocation group along with a descriptive table of the events, and statistical significance will be determined by a chi-square test; other safety data including complications will be tabulated by group but are not expected to be formally analysed.

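### Time to pregnancy has one censoring limit, 270 days, though it is listed for a 450-day assessment as well, and its single Cox hazard ratio depends on the length of follow-up

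*Protocol*

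**What the plan says.** Section 8.2.2.1 (Pregnancy outcomes) opens its list with a general rule: "The following outcomes will be assessed at two time points: 19 months post-randomisation", for conceptions within 270 days, and then "25 months post-randomisation to allow for pregnancy outcomes to be obtained and concern pregnancies conceived within 450 days (approximately 15 months) of randomisation". It gives the purpose of the second assessment: "This will enable us to determine the medium-term effect of the initial treatment policy decision". TTP is one of the listed outcomes, with its own definition: "TTP leading to a live birth defined as time from randomisation to pregnancy in days (censored at 270 days". No 450-day limit for TTP appears anywhere else in the protocol.

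Section 2.2.1 makes TTP leading to a live birth a secondary objective. It lists separately the objective "To compare outcomes of couples over a longer period of 25 months post-randomisation when further interventions may have been provided".

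Section 14.2.2 fixes the method: "Time-to-event outcomes (e.g. TTP leading to a live birth) will be analysed using a mixed effects ('frailty') Cox Proportional Hazard model", with centre as a random effect. The summary is also fixed: "The treatment effect will be expressed as adjusted hazard ratio with 95% confidence interval".

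The timing comes from elsewhere. Section 7.1 starts both interventions within 3 months of randomisation. The notes to the schedule of assessments (section 9.1) place the three IUI cycles at about months 2 to 6 and hold back IVF in the IUI arm until day 270.

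**The concern.** There are two linked difficulties.

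The first is textual. An outcome assessed for conceptions up to day 450 cannot also be censored at day 270 without losing the period that the later assessment was added to cover. In the IUI arm, that period is when most of the follow-on IVF is expected.

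The second concerns the summary measure. One IVF cycle early on is compared with three IUI cycles spread over several months and then IVF. Conceptions in the IVF arm come early and then thin out, while those in the IUI arm keep arriving. A single hazard ratio averages a period well below 1 with periods above 1, and the weights depend on when follow-up stops. The choice of censoring date therefore affects the direction of the reported effect, which is why the missing limit matters more here than it would for most secondary outcomes.

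At stake is the answer to a stated secondary objective and to one of the three high-priority concerns of the patient group in section 1.2.1: how much later couples conceive under the IUI policy, and how many have conceived by a given time.

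**Working it through.** **Text side by side.** The list's rule gives two windows, 270 and 450 days, and the second is said to "concern pregnancies conceived within 450 days (approximately 15 months) of randomisation". The TTP entry gives one limit, 270 days. If that limit applies at both assessments, the 25-month TTP dataset contains the same events as the 19-month one.

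**Inputs from the protocol.** Section 14.1 gives IVF success of 28% and IUI success of 6.4% per cycle (non-inferiority margin case) or 10.36% per cycle (equal-success case). These reproduce the protocol's three-cycle totals: 1 − 0.936³ = 18.0% and 1 − 0.8964³ = 28.0%. The protocol gives no TTP figure to reproduce.

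**Assumptions not in the protocol.** First-cycle conceptions fall on days 28-106 (mean 67). IUI cycles are 50-70 days apart (means 67, 127 and 187). Follow-on IVF in the IUI arm leads to conception on days 284-374 (mean 329), at 28%, with full uptake unless stated. The section 14.1 rates are used for any conception leading to live birth.

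**Early hazard ratio, first cycle alone.** This is ln(1 − p)/ln(1 − 0.28):
- 6.4%: −0.0661/−0.3285 = 0.20
- 10.36%: −0.1094/−0.3285 = 0.33

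**Restricted mean difference to day 270.** Each conception saves (270 − day) days.
- IVF saves 0.28 × 203 = 56.8 days.
- IUI at 6.4% saves 0.0640 × 203 + 0.0599 × 143 + 0.0561 × 83 = 26.2 days. Difference: 30.6 days later with IUI.
- IUI at 10.36% saves 0.1036 × 203 + 0.0929 × 143 + 0.0833 × 83 = 41.2 days. Difference: 15.6 days later with IUI.

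**Share of IUI-arm conceptions to day 450 that fall after day 270.**
- 6.4%: follow-on IVF gives 0.820 × 0.28 = 0.230, and 0.230/(0.180 + 0.230) = 56%.
- 10.36%: 0.720 × 0.28 = 0.202, and 0.202/(0.280 + 0.202) = 42%.

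**Simulation (20,000-40,000 couples per arm, Cox model, IUI versus IVF).** Natural conception, where included, is 0.0002 per day. Further frozen transfers in the IVF arm, where included, are for 30% or 60% of couples not pregnant by day 150, at 25% success on days 150-400.

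| Scenario | Per cycle | HR to day 106 | HR to day 270 | HR to day 450 | Mean difference to 270 (days) | Mean difference to 450 (days) |
|---|---|---|---|---|---|---|
| No natural conception or further transfers | 6.4% | 0.23 | 0.55 | 1.38 | 30.7 | 20.0 |
| | 10.36% | 0.41 | 0.89 | 1.61 | 16.0 | −7.1 |
| Same, 80% uptake of follow-on IVF | 6.4% | 0.25 | 0.57 | 1.19 | 30.0 | 25.1 |
| | 10.36% | 0.41 | 0.91 | 1.51 | 15.4 | −4.4 |
| Natural conception | 6.4% | 0.29 | 0.60 | 1.23 | 30.1 | 21.7 |
| | 10.36% | 0.44 | 0.90 | 1.49 | 15.7 | −6.6 |
| Natural conception, 30% further transfers | 6.4% | 0.30 | 0.58 | 1.08 | 30.9 | 28.4 |
| | 10.36% | 0.44 | 0.85 | 1.30 | 16.4 | 0.8 |
| Natural conception, 60% further transfers | 6.4% | 0.29 | 0.52 | 0.92 | 32.9 | 38.9 |
| | 10.36% | 0.44 | 0.79 | 1.13 | 17.8 | 9.7 |

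The hazard ratio on days 106-270 is 1.4 to 6.8, and on days 270-450 it is 2.9 to 10.7, wherever the IVF arm has later events. Without natural conception or further transfers, the IVF arm has no events after the first-cycle window and the later ratio is undefined. In the equal-success case without further transfers, both arms reach about the same cumulative conception by day 270, yet the overall hazard ratio is about 0.9.

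**The case against.** The bracketed 270 days may have been meant for the 19-month assessment only, with 450 days implied by the list's opening sentence. That is plausible, but the text does not say it and gives no second limit, so the entry needs a clause under either reading. A reader might infer that conceptions on days 271-450 will be lost. The documents do not support this: the section 9.1 schedule collects outcomes at month 25 for all couples who conceive within 450 days. The gap is in the analysis definition, not in data collection.

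On the Cox model, section 14.2 calls its text a brief outline and defers detail to a separate statistical analysis plan. Proportionality checks and curves commonly sit there, and their absence from the protocol is no error. That stands. What the protocol does fix is the effect measure, and the non-proportionality can be foreseen from the schedules.

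A reader might also conclude that the hazard ratio is meaningless and should be replaced. That goes too far. It is an average over a stated follow-up period, and the restricted mean depends on the horizon as well: at 10.36% per cycle it moves from +15 to +18 days at day 270 to between −8 and +10 days at day 450. Its advantage is that it does not assume proportional hazards and that its horizon is explicit.

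Finally, the sizes rest on assumed timing, uptake and later conceptions. The hazard ratio does not cross 1 in every case: at 6.4% with 60% further transfers it goes from 0.52 to 0.92. Follow-on IVF has no bearing on the 270-day result if it is held back until day 270. Sections 7.1.1 and 15.2 word that timing differently from section 9.1, so the claim here is only that most, not all, follow-on IVF falls after day 270.

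**Conclusion.** The point holds in two parts of unequal weight.

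The censoring limit is wrong as written for the 25-month assessment. This rests on the text alone. On the protocol's rates with full uptake of follow-on IVF, 42% to 56% of IUI-arm conceptions up to day 450 would fall outside the stated limit.

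The single hazard ratio is an incomplete summary. Under the assumptions above it is about 0.2 to 0.45 in the first-cycle window and above 1 later, and the overall value depends on where follow-up stops. The directions follow from the schedules; the exact values do not come from the protocol.

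A reader might infer that the medium-term policy result fails. It does not: live birth at 34 weeks or later among conceptions within 450 days is a separate binary analysis and is untouched. Section 14.2 treats all secondary outcomes as exploratory. The primary non-inferiority conclusion and the total of 942 couples are unaffected.

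**What to change.** In section 8.2.2.1, state that TTP is censored at 270 days for the 19-month assessment and at 450 days for the 25-month assessment.

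In section 14.2.2 or the statistical analysis plan, keep the frailty Cox hazard ratio. Beside it, report cumulative-incidence curves by arm and the difference in restricted mean time to conception leading to live birth, to day 270 and to day 450, with 95% confidence intervals. State the follow-up period next to each hazard ratio.

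The cost is one clause of wording and a small amount of extra analysis, with no new data. The downside is that restricted mean time is less familiar to readers than a hazard ratio.

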#### Outcomes in live births≥24 weeks

The following outcomes will be assessed at two time points: 19 months post-randomisation to allow for pregnancy outcomes to be obtained and concern pregnancies conceived within 270 days (approximately 9 months) of randomisation; and 25 months post-randomisation to allow for pregnancy outcomes to be obtained and concern pregnancies conceived within 450 days (approximately 15 months) of randomisation. This will enable us to determine the medium-term effect of the initial treatment policy decision.

- Gestational age at delivery;
- Gestation<28 weeks;

- Gestation<32 weeks;

- Gestation<37 weeks;

- Birthweight, grams;
- Small for gestational age (<10th centile);

- Mode of birth (unassisted vaginal, instrumental vaginal, elective caesarean section, emergency caesarean section);
- APGAR<7 out of 10 at 1 minute;

- APGAR<7 out of 10 at 5 minutes;

- APGAR<7 out of 10 at 10 minutes;

- Survival at 28 days (or discharge from hospital whichever is sooner).

## **Complications**

The following outcomes will be assessed:

i.) for the first IVF treatment within 450 days post randomisation for a period of 60 days following the date of FSH injection;

- ii.) for the first three IUI cycles within 450 days post randomisation for a period of 30 days following the date of ovarian stimulation for partial or cancelled cycles, or date of insemination for complete cycles.
  - Ovarian hyperstimulation syndrome (mild, moderate, severe);
  - Pelvic infection;
  - Bleeding post oocyte retrieval (IVF only);
  - o Admission to High Dependency Unit (HDU)/ Intensive Therapy Unit (ITU), standard ward admission, A&E visit or Outpatient review.

The following outcomes will be assessed at 28 days post birth (or patient's discharge date from hospital whichever is sooner).

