## Additional notes on Error! Reference source not found.

- Months 2-6 are an approximation for when couples will have the three cycles of IUI; this process may be longer.
- X Couples randomised to IUI but progress to IVF as part of clinical care. All couples randomised to IUI cannot progress to subsequent IVF treatment until 270 days (approximately 9 months) post randomisation.
- X to measure outcomes for all couples who conceive within 450 days of randomisation.
- X³- one Clinical Pregnancy Outcome CRF to be completed per positive pregnancy test.
- X- to be completed for each pregnancy conceived during the trial outside of IVF or IUI treatment.
- X one Post-Treatment CRF to be completed 8 weeks after treatment starts (defined as the first day of ovarian stimulation).
- The qualitative sub-studies will approach participants at the indicated timepoints, but their interviews will happen in the subsequent weeks.
- X- measured during the first treatment cycle of IUI and/or IVF. The ideal timepoint during a treatment cycle to collect these questionnaires is between the date of insemination and the date of the pregnancy test for couples undergoing IUI, and between the date of embryo transfer and the date of the pregnancy test for couples undergoing IVF.

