11.2. Case Report Form (CRF) completion

The CRFs will include (but will NOT be limited to) the Forms shown in **Error! Reference source not found.** 

**Table 6**: Case report forms in UNiTY

Form Name	Schedule for submission
Informed Consent Form (one for each partner)	Prior to randomisation
Screening CRF	Prior to randomisation
Baseline CRF	Prior to randomisation
Baseline participant questionnaire: - EQ-5D-5L	Prior to randomisation
Treatment CRFs: - IVF treatment CRF - IUI treatment CRF - Laboratory CRF - Frozen Transfer CRF	During or as soon as possible after treatment
Outcomes CRF: - Post-treatment CRF	8 weeks after treatment starts (defined as the first day of ovarian stimulation) in order to capture all potential complications/outcomes.
Outcomes CRF: - Clinical Pregnancy outcome CRF	As soon as possible after each follow up assessment time point (19 months and 25 months post randomisation)
Outcome participant questionnaires  - EQ-5D-5L (one questionnaire to be completed for each partner)  - CSQ-8 (one questionnaire to be completed for each partner)  - Health resource use (one questionnaire to be completed per couple)	As soon as possible after each follow up assessment time point (during the first treatment cycle of IUI and/or IVF, 19 months and 25 months post randomisation)
Non-trial treatment form	During or as soon as possible after treatment
Natural pregnancy notification CRF	As soon as possible after becoming aware of participant's pregnancy
Serious Adverse Event Form	If expedited: emailed within 24 hours of site research team becoming aware of event If non-expedited: emailed within 4 weeks of site research team becoming aware of event
Change of Status Form	As soon as possible after the point of reduced participation
Deviation Form	As soon as possible after a protocol deviation has occurred

A CRF should be completed for each couple or individual participant as documented at the top of each document. CRFs repeat to account for multiple treatment cycles and multiple pregnancies.

In all cases it remains the responsibility of the PI to ensure that the CRF has been completed correctly and that the data are accurate. This will be evidenced by the signature of the PI, or delegate(s). The Site Signature & Delegation Log will identify all those personnel with responsibilities for data collection.

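### Complications are counted from different start points and for different lengths of time in IVF and IUI cycles, so the rates are not on a common basis and the direction of any imbalance depends on the unit

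*Protocol*

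**What the plan says.** Section 8.2.2.1 (Complications) lists OHSS, pelvic infection, admissions, A&E visits and outpatient reviews for both treatments, plus bleeding after oocyte retrieval for IVF only. It sets the counting rule by type of treatment, not by arm:

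- IVF is counted "for the first IVF treatment within 450 days post randomisation for a period of 60 days following the date of FSH injection".
- IUI is counted over the first three cycles within 450 days, "for a period of 30 days following the date of ovarian stimulation for partial or cancelled cycles, or date of insemination for complete cycles".

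The form that collects these events has its own timing. The notes to the schedule in Section 9.1 call for "one Post-Treatment CRF to be completed 8 weeks after treatment starts (defined as the first day of ovarian stimulation"), and Table 6 in Section 11.2 says this timing is chosen "in order to capture all potential complications/outcomes". Neither place distinguishes the arms.

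Secondary objective 3 in Section 2.2.1 is "To compare the complication rates of the two treatment arms". Section 14.2.2 says that "other safety data including complications will be tabulated by group but are not expected to be formally analysed". No section gives a reason for the different windows, or says whether rates are per cycle, per couple or per covered day.

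**The concern.** The windows differ in both start and length. The IVF window covers stimulation, egg collection and, with a fresh transfer, several weeks of early pregnancy. The window of a completed IUI cycle opens only at insemination and closes 30 days later. The IUI rule is also uneven within itself: an event during letrozole counts if the cycle is later cancelled, but not under that cycle's own window if the cycle is completed.

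This matters because Section 1.1.4 gives lower risk as part of the case for IUI, and Section 10.3 relies on the outcome measures to capture related adverse events as complications. Unequal counting therefore reaches the main tabulation of non-serious safety events. A difference between arms in that table could reflect the counting rule, and so could the absence of one.

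**Working it through.** **1. Per cycle, conceiving, fresh transfer.** Inputs are 60 days from FSH and 30 days from insemination (Section 8.2.2.1). The protocol does not give the time from the first FSH injection to egg collection, so I assume 10-14 days. I also read the date of FSH injection as the first one.

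- IVF days after egg collection: 60 − 14 = 46, to 60 − 10 = 50.
- IUI days after insemination: 30.
- Difference: 46 − 30 = 16, to 50 − 30 = 20 days.
- Gestation at close, (days + 14)/7: IVF (46 + 14)/7 = 8.6 to (50 + 14)/7 = 9.1 weeks; IUI (30 + 14)/7 = 6.3 weeks.

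An A&E visit at 7-8 weeks of pregnancy is therefore counted after IVF and not after IUI. Earlier unsuccessful IUI cycles do not change that.

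**2. Stimulation phase of a completed IUI cycle.** With letrozole from day 2 and tracking from about days 10-12 (Section 7.1.1), roughly 10-12 days pass before insemination (assumption). None of them fall in that cycle's own window. For the first cycle they are always lost. For later cycles the previous window may catch them by chance. If cycles run back to back at 28 days (assumption), the next stimulation starts 28 − 12 = 16 to 28 − 10 = 18 days after the previous insemination, inside its 30 days. At the roughly two-month spacing shown in Table 2 it does not.

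**3. Per couple.** The 30 days apply to each cycle, since the start is set by whether that cycle was completed. First, the protocol's own cycle counts (Section 14.1, Tables 7 and 8), with per-cycle success p and expected cycles = 1 + (1 − p) + (1 − p)²:

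- p = 0.064: 1 + 0.936 + 0.876 = 2.812, matching 281.2 per 100 couples.
- p = 0.1036: 1 + 0.8964 + 0.8035 = 2.700, matching 270.

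(The couples row printed in Table 7 sums to 100 + 89.6 + 80.4 = 270.0; the total of 281.2 is the one that fits 6.4%.)

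Covered days per IUI couple, with overlaps not removed:

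- 30 × 2.812 = 84.4, which is 1.41 times 60.
- 30 × 2.700 = 81.0, which is 1.35 times 60.

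A first IVF in the IUI arm within 450 days adds 60 more. As an upper case, if every couple without a live birth had one:

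- 84.4 + 60 × 0.936³ = 84.4 + 49.2 = about 134 days.
- 81.0 + 60 × 0.8964³ = 81.0 + 43.2 = about 124 days.

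**4. Effect of the window alone.** Assume a constant background event risk h per 30 days, the same in all phases. The protocol gives no such figure, so a range is shown. Probability of at least one event = 1 − (1 − h)^(days/30).

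| h | One IUI cycle (30 d) | One IVF (60 d) | Three IUI cycles (90 d) | Three IUI + one IVF (150 d) |
|---|---|---|---|---|
| 1% | 1.0% | 2.0% | 3.0% | 4.9% |
| 3% | 3.0% | 5.9% | 8.7% | 14.1% |
| 5% | 5.0% | 9.8% | 14.3% | 22.6% |

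With identical underlying risk, IUI looks safer per cycle and less safe per couple after three cycles.

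**5. Form against window.** 8 weeks = 56 days, so the nominal IVF window runs 60 − 56 = 4 days past the form date.

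**The case against.** The strongest reply is that the protocol's objective compares arms, and analysis is as randomised (Section 14.2). At that level the IUI arm has more covered time, so a reader who infers from 60 against 30 days that the comparison is biased against IVF overall has the wrong unit. That reply stands. Bias against IVF would need a per-cycle rate, which the protocol does not specify.

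Other parts of the reply also carry weight:

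- The 16-20 day figure needs a fresh transfer. Section 7.1.2 also allows a frozen one. If that takes place in a later cycle, the 60 days from FSH may end around or before the pregnancy test, and the gap shrinks or reverses.
- Miscarriage and ectopic pregnancy are separate outcomes without the 30- or 60-day limit (Section 8.2.2.1). Adverse event reporting runs in both arms from the start of the intervention to 60 days after the cycle outcome is known (Section 10.3), and serious events not reported as SAEs go on CRFs (Section 10.4.1). Serious events outside the window are therefore not lost to the trial, though they may be absent from the complication table.
- Complications are tabulated without a formal test, and secondary outcomes are exploratory.
- Table 2 marks complications on the Post-Treatment CRF at several months, so it is not certain that days 57-60 go unrecorded.

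What the reply does not remove is the difference in what is covered. Extra IUI cycles add days after unsuccessful inseminations. They do not extend follow-up in the conceiving cycle, and they recover the stimulation phase only if cycles happen to run close together.

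**Conclusion.** The point holds as a lack of common ascertainment. Start and length both differ without a stated reason. The stimulation phase of a completed IUI cycle is outside its own window, and in a conceiving cycle with fresh transfer IVF is followed about 16-20 days longer (given egg collection 10-14 days after the first FSH injection). Per cycle the rule favours IUI. Per couple the IUI arm has about 81-84 covered days against 60, on the protocol's cycle counts and with 30 days applied per cycle, plus any later first IVF.

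The documents do not support a claim of overall bias in either direction, because the unit is not stated. No non-inferiority conclusion depends on this table. The change is worth making because the comparison is a named objective and, as it stands, the tabulated rates cannot be read without knowing the denominator.

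**What to change.** In Section 8.2.2.1:

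- Start the window at the first day of ovarian stimulation (first letrozole dose or first FSH injection) for every counted cycle, whether complete, partial or cancelled.
- Use the same end point after that day for both treatments, aligned with the 8-week Post-Treatment CRF. Reconcile the 60-day IVF window with the 56-day form.
- Count an event once where IUI windows overlap.
- Tabulate by randomised arm, per couple (primary) and per cycle started, and show covered days beside each rate.

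The cost is mainly wording, since the form is already timed from stimulation in both arms. Its content is not shown in the protocol, so confirm that it records event dates.

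The change has a downside. At 56 days per cycle, covered time in the IUI arm rises to 2.812 × 56 = 157 or 2.700 × 56 = 151 days before overlaps are removed, against 56 for one IVF. With back-to-back 28-day cycles (assumption) and overlaps counted once, it is 56 + 28 × 1.812 = 107 or 56 + 28 × 1.700 = 104 days, still about 1.9 times the IVF window. The per-couple rate must therefore be read as the burden of the whole policy, and this is why covered days and the per-cycle rate belong beside it.
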